Official Title : Efficacy of Light Therapy in Improving Sleep Quality, Fatigue, and Emotional Symptoms in Patients with Gynecologic Cancer

NCT 編號 : Pending

Document Date : 2024.12.15

Efficacy of Light Therapy in Improving Sleep Quality, Fatigue, and Emotional Symptoms in Patients with Gynecologic Cancer

Abstract

Objective: This study aims to examine the efficacy of light therapy in improving sleep quality, reducing fatigue, and alleviating emotional symptoms among patients diagnosed with gynecologic cancer.

Methods: A randomized controlled trial was conducted at a medical center in northern Taiwan. Participants were eligible if they were aged 18 years or older, had a physician-confirmed diagnosis of gynecologic cancer, and reported an Insomnia Severity Index – Chinese version (ISI-C) score of ≥ 9 . Eligible participants were randomly assigned to either an experimental group or a control group ($n = 47$ per group). At baseline (T0), participants completed a demographic questionnaire, ISI-C, the Brief Fatigue Inventory – Taiwanese version (BFI-T), and the Distress Thermometer (DT). The experimental group received daily morning light therapy for 30–40 minutes over four weeks using a circadian-regulating light device. The control group continued their usual routines during the same period. Follow-up assessments were scheduled at day 7 (T1), day 14 (T2), day 21 (T3), and day 28 (T4). Data will be analyzed using generalized estimating equations (GEE) to evaluate the effects of the intervention on sleep quality, fatigue, and emotional symptoms.

Keywords: light therapy, gynecologic cancer, chemotherapy, sleep quality, fatigue, emotional symptoms.

Research Motivation and Significance

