This study was conducted at a tertiary medical center in northern Taiwan between May 13 and December 12, 2024. Eligible participants were individuals aged 18 years or older with a physician-confirmed diagnosis of gynecologic cancer and an Insomnia Severity Index-Chinese version (ISI-C) score of 9 or above. All participants provided written informed consent prior to enrollment. Exclusion criteria included the presence of visual impairment or photosensitivity that could interfere with the use of light therapy devices, a current diagnosis of psychiatric disorders or cognitive impairment, and any physical limitations that would hinder adherence to the intervention protocol or data collection due to disease severity.

Sample Size Calculation and Randomization

Sample size was calculated using G*Power 3.1, assuming a medium effect size ($f = 0.25$), a significance level of $\alpha = 0.05$, and a statistical power of 0.80 for a two-group comparison. The estimated minimum sample size was 78 participants. Allowing for an anticipated attrition rate of 20%, the target enrollment was increased to 94 participants. Participants were randomly assigned to either the experimental or control group in a 1:1 ratio using the random number generator function in Microsoft Excel (Microsoft Corporation, Redmond, WA, USA). Each group ultimately included 47 participants.

Data Collection and Ethical Considerations

Ethical Approval and Informed Consent : The study protocol was approved by the Institutional Review Board (IRB) of the participating medical center (CGH-IRB No. 202400345A3C601). Participant recruitment was conducted in the gynecologic outpatient department. Before enrollment, all participants received a thorough explanation of the study's objectives, procedures, potential risks, and anticipated benefits. They were assured that their personal data would be anonymized, securely stored, and used solely for academic research purposes. Participants were informed of their right to withdraw from the study at any time without affecting their ongoing clinical care. Written informed consent was obtained from all participants.

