All statistical analyses were performed using IBM SPSS Statistics version 26.0. To evaluate baseline homogeneity between the experimental and control groups, independent samples t-tests were used for continuous variables, while chi-square (χ^2) tests or Fisher's exact tests were applied for categorical variables, as appropriate. The effectiveness of the light therapy intervention on sleep quality, fatigue, and emotional distress across time points was assessed using generalized estimating equations (GEE), which account for correlated repeated measures and accommodate missing data. Statistical significance was set at a two-tailed p value of < 0.05 .

Results

A total of 94 participants diagnosed with gynecologic cancer were enrolled and randomly allocated into the experimental and control groups with a 1:1 ratio (47 per group). During the study period, four participants withdrew due to health-related reasons, resulting in a final sample size of 90 (44 in the experimental group and 46 in the control group). The mean age was approximately 52 years. Baseline demographic and clinical characteristics were analyzed to ensure group equivalence. All variables were comparable between groups, except for body mass index (BMI), which showed a statistically significant difference and was adjusted for in subsequent analyses.

Primary and Secondary Outcomes :

Participants completed outcome assessments at baseline and weekly intervals for four weeks following the intervention (T1–T4). Sleep quality was assessed using the

Insomnia Severity Index – Chinese version (ISI-C).Fatigue was evaluated using the Brief Fatigue Inventory – Taiwan version (BFI-T).Emotional distress was measured using the Distress Thermometer (DT).All instruments were administered at baseline (T0), and at days 7 (T1), 14 (T2), 21 (T3), and 28 (T4).

Changes in these outcomes across timepoints and between groups were analyzed using generalized estimating equations (GEE), with BMI included as a covariate to adjust for baseline differences. This model allowed for evaluation of group, time, and interaction effects on outcome measures.

References

Çelik, A., & Usta Yeşilbalkan, Ö. (2023). The Effect of the Bright White Light Application to Cancer Patients Receiving Palliative Care on Their Fatigue Level and Sleep Quality: A Randomized Control Trial. *Omega*, 88(1), 303–317. <https://doi-org.libermg.cgmh.org.tw:8443/10.1177/00302228221093462>

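### ISI-C, BFI-T and DT are each tested at an unadjusted two-sided 0.05 with no primary outcome, visit or model term named; the chance of at least one false-positive outcome is about 8–14%

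*Combined protocol and SAP*

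**What the plan says.** The Abstract's objective puts the three aims side by side: efficacy "in improving sleep quality, reducing fatigue, and alleviating emotional symptoms among patients diagnosed with gynecologic cancer". Each aim has its own instrument (ISI-C, BFI-T, DT), measured at T0 and at four weekly follow-ups, T1 to T4.

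The Statistical Analysis section gives one rule for all of them: "Statistical significance was set at a two-tailed p value of" less than 0.05. Under Results, the heading "Primary and Secondary Outcomes" is followed by the three instruments without saying which is primary and which secondary. On the model, that section says: "Changes in these outcomes across timepoints and between groups were analyzed using generalized estimating equations (GEE), with BMI included as a covariate". It adds: "This model allowed for evaluation of group, time, and interaction effects on outcome measures". No term, contrast or visit is marked as the one that decides efficacy. The only adjustment mentioned is for BMI, which has no bearing on multiplicity.

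The sample-size section uses one alpha of 0.05 and "a statistical power of 0.80 for a two-group comparison", without naming an outcome. The Results section reports attrition, "resulting in a final sample size of 90 (44 in the experimental group and 46 in the control group"), but no outcome result by group.

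**The concern.** The heading promises a ranking that the text does not supply. A reader cannot tell in advance which result would count as the trial's efficacy finding. Followed as written, the plan lets any of three outcomes be presented as that finding. It also does not rule out choosing among four follow-up visits, or between the group effect and the group-by-time interaction.

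This concerns the set of tests, not any one of them. If light therapy did nothing, each test alone would still be significant 5% of the time, but the chance that at least one outcome gives something to report is higher. The plan neither states that chance nor limits it. Naming a primary after seeing outcomes by group would not repair this.

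**Working it through.** **The plan's own figure.** The sample-size section gives this result: "The estimated minimum sample size was 78 participants". With f = 0.25, alpha = 0.05 and two groups, a between-group repeated-measures F test has noncentrality λ = N f² m / (1 + (m − 1)ρ) on 1 and N − 2 df. Neither m (number of measurements) nor ρ (correlation between them) is stated.

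- m = 5, ρ = 0.5: λ = 78 × 0.0625 × 5/3 = 8.125; power 0.804.
- m = 3, ρ = 0.4: λ = 78 × 0.0625 × 3/1.8 = 8.125; power 0.804.

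So 78 can be reproduced, but not from a unique setting. It says nothing about which outcome or test was meant and is not used below.

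**Inputs for the error rate.** From the document: three outcomes, two-sided 0.05 each, no adjustment. Assumed: no true effect, exactly one between-group test per outcome, approximately normal test statistics, and a common between-outcome correlation ρ. The document gives no correlation, so a range is shown.

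**Formula.** Write Zᵢ = √ρ·U + √(1 − ρ)·eᵢ for i = 1, 2, 3, with U and eᵢ independent standard normal and c = 1.96. Then

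P(at least one significant) = 1 − ∫ φ(u) [Φ((c − √ρ u)/√(1 − ρ)) − Φ((−c − √ρ u)/√(1 − ρ))]³ du.

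For false benefit only, omit the second Φ term. At ρ = 0 the two reduce to 1 − 0.95³ = 1 − 0.8574 = 14.3% and 1 − 0.975³ = 1 − 0.9269 = 7.3%.

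| Assumed correlation | Either direction | False benefit only |
|---|---|---|
| 0 | 14.3% | 7.3% |
| 0.3 | 13.6% | 6.8% |
| 0.5 | 12.5% | 6.3% |
| 0.7 | 10.9% | 5.5% |
| 0.8 | 9.8% | 4.9% |
| 0.9 | 8.4% | 4.2% |
| One test only | 5.0% | 2.5% |

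Testing the smallest p value at 0.05/3 = 0.0167, as Holm does first, brings the either-direction rate to 4.9% at correlation 0 and 3.0% at 0.9.

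**Power cost of the first Holm step.** Take 44 against 46 and a true difference of 0.5 SD at T4 (assumed), tested on change from T0. The SD of change is √(2(1 − r)) in units of the outcome SD, where r is the T0–T4 correlation (assumed). The noncentrality is 0.5/√(2(1 − r)) × √(44 × 46/90), with √22.49 = 4.742, on 88 df.

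- r = 0.5: 0.5/1 × 4.742 = 2.371; power 65% at 0.05, 48% at 0.0167.
- r = 0.7: 0.5/0.7746 × 4.742 = 3.061; power 86% at 0.05, 73% at 0.0167.

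**The case against.** The strongest defence is that no stated error rate is breached. The plan sets 0.05 per test and never claims familywise control; reporting three separately named outcomes, each on its own terms, is defensible if labelled that way. That stands, and it limits the point. A reader might infer that the individual p values are invalid or that a promised 5% overall rate is broken; the document supports neither. What remains is that the plan does not label its tests and leaves open which one is the efficacy claim.

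A second defence is that ISI-C is the primary in substance: a score of 9 or above is the entry criterion, and sleep quality comes first in the title and objective. That is a good reason to choose it, but the document does not designate it. A primary may be recorded in a registry entry (the NCT number is shown as pending), so the point covers this document only.

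Three stronger readings are tempting.

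- *That the error rate is far above 14%.* Six independent tests (three outcomes, two between-group terms) would give 1 − 0.95⁶ = 26.5%, and twelve (three outcomes, four visits) 1 − 0.95¹² = 46.0%. Correlation lowers both. The text does not rule such counting out, but it does not say that any visit or term may count, so these are not the size of the problem.
- *That the minimum of 78 shows one test on one outcome was intended.* It does not: more than one unstated setting gives 78, and a per-test 0.05 also fits sizing each outcome separately.
- *That a primary was left open so it could be picked after unblinding the results.* The timing cannot be settled. The header is dated 15 December 2024, but the reference list includes an item dated 19 December 2024 and 2025 publications. The Abstract puts the analysis in the future, the Results section in the past.

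**Conclusion.** The concern holds in a limited form. The document tests three outcomes at an unadjusted two-sided 0.05, ranks none of them despite its heading, and names no decisive visit or model term. With one between-group test per outcome, the chance under no effect of at least one significant outcome is about 11–14% at between-outcome correlation 0–0.7 and 8–10% at 0.8–0.9. For false benefit it is 5.5–7.3% and 4.2–4.9%, against 2.5%.

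These figures assume no effect on any outcome, normal test statistics and a common correlation. The conclusion does not depend on where in the range the correlation lies: even at 0.9 the rate is more than half as high again as 5%. It would be higher if several visits or terms could count. Following the plan as written therefore gives a less interpretable result than a plan with one named test and a rule across outcomes.

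**What to change.** 1. Name one between-group test, the same for all three outcomes: for example change from T0 at T4, average T1–T4 change from T0, or the joint group-by-time test. Fix it in a dated record without reference to results by group. Which test has most power depends on the correlation between visits and the shape of the effect, so none is preferred here.
2. If a dated record shows that outcomes had not been examined by group, choose one of two rules. Either make ISI-C the sole primary at 0.05, because insomnia severity defines entry and sleep quality is listed first, and test BFI-T and DT only after it succeeds, by Holm (0.025, 0.05). Or apply Holm across all three outcomes (0.0167, 0.025, 0.05).
3. If outcomes had already been examined by group, or no record can show otherwise, name no confirmatory primary. Report the same tests for all three outcomes, label them exploratory and state that the p values are unadjusted. Holm does not apply on this branch.
4. In every case, report the other visits and model terms as estimates with confidence intervals, without efficacy claims.

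**Cost.** The text change is short, plus a record of who had seen outcomes by group and when. ISI-C as sole primary costs ISI-C no power; BFI-T and DT can then be claimed only if ISI-C succeeds. Holm across the three lowers power per outcome at its first step: under the assumptions above, from 65 to 48% at T0–T4 correlation 0.5 and from 86 to 73% at 0.7. The exploratory branch costs no power but gives up the confirmatory claim.

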Baseline Assessment and Intervention : Following consent, participants completed baseline assessments (T0), including a demographic and treatment questionnaire, the Insomnia Severity Index – Chinese version (ISI-C), the Taiwanese version of the Brief Fatigue Inventory (BFI-T), and the Distress Thermometer (DT). Participants randomized to the experimental group were instructed to wear the Re-Timer® circadian regulator glasses for 30–40 minutes each morning within 30 minutes of waking, for four consecutive weeks. Participants recorded daily light therapy duration and sleep hours. If any discomfort occurred during the intervention, therapy was discontinued immediately, and support was provided by the research team. The control group was instructed to continue their regular daily routines without any light therapy intervention.

Follow-up Assessments : Outcome measures (ISI-C, BFI-T, and DT) were reassessed via an online questionnaire delivered through the LINE messaging app on Days 7 (T1), 14 (T2), 21 (T3), and 28 (T4) after the start of the intervention

Measurement Instruments

Demographic and Treatment-Related Variables :

Data collected included participants' age, body mass index (BMI), education level, marital status, religious affiliation, employment status, cancer type, cancer stage, use of sleep medications, and history of emotional distress. Treatment-related variables encompassed the current treatment modality, time since treatment completion, and general health status.

Sleep Quality :

Sleep quality was assessed using the Chinese version of the Insomnia Severity Index (ISI-C), which evaluates the severity and impact of insomnia symptoms over the past two weeks. The seven items cover:

Difficulty initiating sleep

Difficulty maintaining sleep

Early morning awakening

Satisfaction with current sleep pattern

Interference with daily functioning

Noticeable impairment in quality of life due to sleep problems

Degree of worry or distress about sleep difficulties

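### After four post-randomisation withdrawals the only sample given is 90, which reads as a completer analysis rather than an analysis of all 94 as randomised

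*Combined protocol and SAP*

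**What the plan says.** The opening of Results says that 94 participants "were enrolled and randomly allocated into the experimental and control groups with a 1:1 ratio (47 per group"). It then reports that four people left the study because of their health, "resulting in a final sample size of 90 (44 in the experimental group and 46 in the control group"). The same paragraph goes straight on to mean age, baseline comparability and the BMI imbalance, and mentions no other sample.

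Statistical Analysis names the method as "generalized estimating equations (GEE), which account for correlated repeated measures and accommodate missing data". Primary and Secondary Outcomes adds that the model gives group, time and interaction effects, "with BMI included as a covariate to adjust for baseline differences".

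Under Data Collection and Ethical Considerations, participants complete T0 after consent, with follow-up questionnaires on days 7, 14, 21 and 28. The four who withdrew should therefore have baseline scores, and some may have follow-up scores.

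The document contains no intention-to-treat statement, definition of the analysis set, timing of the withdrawals, missing-data assumption or sensitivity analysis.

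**The concern.** Randomisation makes the two groups of 47 comparable. It does not do the same for the 44 and 46 who remain after people leave for reasons that may bear on the outcome. Health-related withdrawal is plausibly connected with sleep, fatigue and distress, so taking those people out of the sample weakens the protection that randomisation gives.

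It also sits awkwardly with the choice of method. GEE can use incomplete records, but only if those records stay in the model. Removing a whole person discards the T0 score and any follow-up scores already collected.

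Keeping the records does not settle everything. Standard unweighted GEE assumes that data are missing completely at random, which is doubtful when people leave because of their health. The working correlation and a sensitivity analysis therefore matter too, and the document states neither.

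**Working it through.** **Participant flow.** Inputs are from Results.
- Experimental: 47 − 44 = 3 withdrawn, 3/47 = 6.4% (exact 95% CI 1.3 to 17.5%).
- Control: 47 − 46 = 1 withdrawn, 1/47 = 2.1% (0.1 to 11.3%).
- Overall: 94 − 4 = 90, which reproduces the stated figure; 4/94 = 4.3%.
- Fisher's exact test of 3/47 against 1/47 gives p = 0.62, so the split does not show differential dropout.

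**Shift in a follow-up mean difference.** Let δ be how much worse, in SD units, the withdrawn are than completers in their own arm. The document gives no scores for them, so δ is assumed. Leaving out k of 47 changes an arm's mean by (k/47)δ. With the same δ in both arms, the contrast changes by

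(3/47 − 1/47)δ = 0.0426δ.

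- δ = 0.5: 0.021 SD
- δ = 1.0: 0.043 SD
- δ = 1.5: 0.064 SD

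The sample-size section works from "assuming a medium effect size ($f = 0.25"), which for two equal groups is 2 × 0.25 = 0.5 SD. The shifts are 4% to 13% of that. The standard error of a single-visit contrast at 44 against 46 is √(1/44 + 1/46) = 0.211 SD, so they are 0.10 to 0.30 of a standard error.

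If the withdrawn differed in opposite directions in the two arms, the change is (4/47)δ, or 0.085 SD at δ = 1. If those in the experimental arm were better than completers, the sign can reverse.

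**Shift in the group-by-time effect.** This is the T4 group difference minus the T0 group difference.
- Equally worse at T0 and T4: both differences shift by 0.0426δ and cancel, so leaving the four out causes essentially no bias.
- Worse only after baseline: the full 0.0426δ applies.

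**What restoring the four does if they have T0 scores only.** Take δ = 1 at every visit. Lower scores are better, so a negative change favours light.
- Independence working correlation: the T0 difference rises by 0.043 and the T4 difference is unchanged, so the interaction moves by −0.043 SD.
- Exchangeable correlation of 0.5 (assumed): T4 moves by 0.5 × 0.043 = 0.021, so the interaction moves by 0.021 − 0.043 = −0.021 SD.

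Since leaving them out causes no bias in this case, both movements are away from the truth, and the exchangeable structure halves the error.

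**Power.** For a repeated-measures between-group test, λ = f²Nm/(1 + (m − 1)ρ). With m = 5 visits and ρ = 0.5 (both assumed, as the document states neither as a power input), N = 78 gives power 0.80 and reproduces the stated minimum. Power is 0.857 at N = 90 and 0.872 at N = 94. Power is not the issue.

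**The case against.** The strongest reply is that the document never says the GEE was run on 90. A final sample of 90 could mean the number who finished, and a method chosen because it can "which account for correlated repeated measures and accommodate missing data" fits keeping partial records. This is fair as far as it goes: the completer reading is an inference. It remains the plainer one, because 90 is the only sample given after the withdrawals and the baseline description follows directly from it. The GEE remark does not settle the matter, since it could refer only to missed questionnaires among the 90. If all 94 were in fact analysed, the text still needs to say so.

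The second reply is about size: 4.3% were lost when 20% was allowed for, and the shifts are a fraction of a standard error. That stands.

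Three stronger readings are tempting, and the documents do not support them.
- A reader might infer that every outcome is biased in favour of light therapy. The document gives no scores, timing or specific reasons for the four. The direction rests on assumptions, and for the interaction it depends on when any worsening began.
- A reader might infer that the trial can no longer claim a randomised comparison. That is out of proportion to four losses out of 94.
- A reader might connect the three experimental-arm withdrawals with the rule that "If any discomfort occurred during the intervention, therapy was discontinued immediately". Nothing links them. That rule concerns stopping the glasses, not leaving the study, and one of the four withdrawals was in the control arm.

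**Conclusion.** The point holds in a limited form. As written, the plan randomises 94 and reads as analysing 90 completers, so the comparison is not fully protected by randomisation.

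The likely effect is modest: 0.02 to 0.06 SD in a follow-up mean difference, assuming the withdrawn were 0.5 to 1.5 SD worse than completers by the same amount in both arms, and near zero for the group-by-time effect if they were equally worse at baseline. The direction is not established. The change is worth making because it is inexpensive and removes an ambiguity that a reader cannot resolve from the text.

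**What to change.** 1. Define the primary analysis as all 94 participants in the arm to which they were randomised, using T0 and every available T1–T4 score.
2. State a non-independence working correlation for the GEE (for example exchangeable), or use a likelihood-based repeated-measures model, which needs only missingness at random given the observed data. Independence should be avoided for the reason shown in the working.
3. Replace the single final-sample figure with, by arm, the number randomised, the number contributing data at each visit and the number completing, and give the reason and timing of each withdrawal.
4. Present the 90-person analysis as a sensitivity analysis.
5. Add one shift analysis in which missing experimental-arm scores are made 0.5, 1.0 and 1.5 SD worse. If only those three lack a T4 score, this moves the T4 contrast by (3/47) × 0.5, 1.0 and 1.5, or 0.032, 0.064 and 0.096 SD.

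Research Setting and Participants gives December 12, 2024 as the end of the study, so the fix relies on data already held. The cost is revised wording and one re-run. The estimate may move slightly in either direction.

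### The GEE adjusts for BMI, picked by a baseline test, and names no outcome's own T0 score as a covariate; the likely cost is precision, of a size the documents do not fix

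*Combined protocol and SAP*

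**What the plan says.** Under Primary and Secondary Outcomes: "Changes in these outcomes across timepoints and between groups were analyzed using generalized estimating equations (GEE), with BMI included as a covariate". The next sentence gives the terms: "This model allowed for evaluation of group, time, and interaction effects on outcome measures". No other covariate is named.

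The choice of BMI follows from baseline testing. Statistical Analysis says: "To evaluate baseline homogeneity between the experimental and control groups, independent samples t-tests were used for continuous variables", with chi-square or Fisher tests for categorical variables. Results then reports that all variables were comparable "except for body mass index (BMI), which showed a statistically significant difference and was adjusted for in subsequent analyses".

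All three instruments are given at T0 and again at days 7, 14, 21 and 28. Eligibility requires "an Insomnia Severity Index-Chinese version (ISI-C) score of 9 or above"; BFI-T and DT have no entry cutoff. The analysed sample is 90 (44 experimental, 46 control).

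The text does not state whether T0 is one of the GEE responses, which of the three effects is the treatment effect, whether BMI also interacts with time, or how strongly T0 and follow-up scores are correlated.

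**The concern.** An outcome's own baseline score is usually among its strongest predictors, and here it is already collected. Adjusting for it generally narrows the interval for the treatment effect at almost no cost. The plan instead lets a significance test between randomised arms choose the covariate. Such a test detects chance imbalance and does not show whether a variable predicts the outcome. With the 13 demographic and treatment variables listed under Measurement Instruments, treated as independent, the probability of at least one significant difference by luck is 1 − 0.95^13 = 49%.

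At stake is precision, and so the chance of detecting a real effect on sleep, fatigue or distress. The procedure may have added a term that cannot help the group-by-time contrast while omitting the one likely to help.

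**Working it through.** **1. The plan's own sample size.** The plan gives 78, "assuming a medium effect size" of f = 0.25 with power 0.80. A repeated-measures between-group F test has noncentrality f²·N·m/(1 + (m − 1)ρ). With m = 5 visits and ρ = 0.5 this is 0.0625 × 78 × 5/3 = 8.125 on 1 and 76 df, giving power 0.804, and 78 is the smallest even N reaching 0.80. Three visits with ρ = 0.4 also give 8.125 and 78. A single two-group comparison would need 128. So 78 is reproducible, but the settings are unstated and do not reveal the tested contrast.

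**2. What BMI does.** Take a mean model with a free group difference at each visit plus c × BMI. The BMI term shifts the arm difference by the same amount at every visit, so it cancels from T4 minus T0. GEE fits to simulated complete data with a BMI imbalance confirm this. The T4 interaction was −1.9177 with and without BMI, and its robust SE was unchanged, under independence, exchangeable and AR(1) working correlation. Only the group term moved (0.122 to −0.276 under the first two). With four withdrawals (3 vs 1; 200 simulated trials) the interaction moved by 0.012 SE on average and 0.061 SE at most. A BMI-by-time term would move it (−1.918 to −1.610), but none is named.

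**3. Precision if T0 is a response and group-by-time is tested.** Assumptions not in the documents: T0-to-follow-up correlation ρ, and d = 0.5 in follow-up SDs (f = 0.25 for two equal groups). With equal unit SDs:
- variance of change: 2(1 − ρ)
- T0-adjusted variance: 1 − ρ²
- proportional cut: (1 − ρ)/2

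Power is from the noncentral F with h = 44 × 46/90 = 22.49, noncentrality 0.25h/variance, and 88 df (87 adjusted).

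| ρ | change | adjusted | cut | power |
|---|---|---|---|---|
| 0.3 | 1.40 | 0.91 | 35% | 51% to 69% |
| 0.5 | 1.00 | 0.75 | 25% | 65% to 77% |
| 0.7 | 0.60 | 0.51 | 15% | 86% to 91% |
| 0.9 | 0.20 | 0.19 | 5% | no gain |

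Estimating the T0 slope costs a factor of about 87/86 = 1.012, which the table omits. In 20,000 simulated trials per cell, which include that cost, the cuts were 34%, 23% and 13% at ρ = 0.3, 0.5 and 0.7. Both estimators averaged within 0.003 of the true effect.

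**4. Unequal SDs.** With follow-up SD equal to k times the T0 SD, the cut is (1 − ρk)²/(1 + k² − 2ρk).
- ρ = 0.7, k = 1.2: 0.0256/0.76 = 3%
- ρ = 0.7, k = 0.8: 0.1936/0.52 = 37%
- ρ = 0.5, k = 1.2: 0.16/1.24 = 13%
- ρ = 0.5, k = 0.8: 0.36/0.84 = 43%

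The cut vanishes when ρk, the slope of follow-up on T0, equals 1. Adjustment then loses about 1% through the slope cost.

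**5. ISI-C.** The entry cutoff shrinks the T0 spread. Assume a normal T0 score truncated to its upper share p. Its variance s² is then 0.363 at p = 0.5 and 0.583 at p = 0.8. The cut is (1 − ρ)s²/((1 − ρ)s² + 1 + ρ), with ρ the unselected correlation:
- ρ = 0.5: 11% (p = 0.5) or 16% (p = 0.8); power 65% to 70% or 65% to 73%
- ρ = 0.7: 6% or 9%; power 75% to 78% or 80% to 83%

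The share kept by the cutoff is not in the documents.

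**6. If only T1–T4 are responses.** The T4 variance is 1 without T0 and 1 − ρ² with it, so the loss is ρ²: 9%, 25% and 49% at ρ = 0.3, 0.5 and 0.7. On this reading BMI does affect the group effect.

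**The case against.** The strongest reply is that the interaction already deals with baseline. If T0 is a response, group-by-time compares change from T0, which is a valid estimate. This stands as far as validity goes. A reader might infer from the missing covariate that T0 is ignored or that the effect is biased. The documents do not support either inference: randomisation protects the estimate, and the wording about changes across time points fits T0 as a response. What remains is that a change comparison fixes the T0 slope at 1, which usually costs precision.

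Second, the size rests on assumptions. This stands. The Fatigue section gives a BFI-T test–retest reliability of 0.91, and at a correlation near 0.9 with equal SDs the gain is negligible. That figure is not a T0-to-day-28 correlation in this trial, and BFI-T covers only the past 24 hours, so it does not settle ρ. Nor do the documents support a firm claim of moderate loss for BFI-T and DT, given the SD range in step 4.

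Third, the BMI result is narrow. It concerns the interaction only, with complete data and no BMI-by-time term. A reader might infer that adjusting for BMI damages the treatment estimate. Nothing here shows that, and the harm from the term itself is small.

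Fourth, the tested effect is unsettled. A group effect averaged over T0–T4 is compatible with the sample size and would dilute the effect to 0.8d. That is mainly a choice-of-contrast problem and is not counted here. At ρ = 0.5, power is 68% for that average and 84% for the T1–T4 mean with no T0 covariate at all.

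Fifth, it may be too late. The document is dated 2024.12.15, three days after data collection ended, yet its References cite a release dated December 19, 2024 and articles from 2025, and it contains a Results section. Only the Abstract still speaks of analysis in the future. This stands, and it limits the remedy.

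**Conclusion.** The point holds as a loss of precision together with an incomplete specification. The plan names no outcome's own T0 score, chooses its one covariate by a baseline test, and leaves open both the role of T0 and the tested effect. T0 adjustment would generally help whether or not T0 is a response.

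The documents do not fix the size. It could be substantial for BFI-T and DT at low to middling correlations, and negligible if the slope is near 1. For ISI-C it is about 6% to 16% of variance at ρ from 0.5 to 0.7, if 50% to 80% of the distribution passes the cutoff. The worst-case cost of adjusting is about 1% of variance.

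The structural facts are certain; confidence in the magnitude is medium, since ρ, the SD ratio and the share kept are all assumed. The point merits correction but does not invalidate the stated analysis.

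**What to change.** For each outcome, fit the GEE to T1–T4 with group, time, group-by-time and that outcome's own T0 score. An alternative is to keep T0 as a response with the T0 means constrained equal across arms. Name one tested contrast, such as the group difference at T4. State whether BMI interacts with time in the stated model, and drop baseline significance tests as a way of choosing covariates.

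State when the outcomes were first analysed by group. If that had already happened, as seems probable, keep the stated BMI-adjusted model as the main analysis and report the T0-adjusted model beside it, dated and labelled post hoc. If it had not, report both models and date the change.

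The cost is a few lines of SAP text, a rerun in the same software and a dated disclosure. No new data are needed.
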